4.1. Design

The proposed study is a randomized control pilot trial of at least 60 and up to 70 women newly diagnosed with early-stage breast cancer who are finishing primary treatment. Participants will be randomized either to the intervention arm (CCC website that will provide information on team-based follow-up care for both cancer surveillance and preventive care) or the control arm (static online survivorship care plan template which was adapted from the ASCO breast cancer survivorship template). The feasibility and acceptability of the tool and correlations with patient-reported outcomes will be assessed 3 months following the completion of the baseline survey. A sample of 8-10 patients in the intervention arm will then be invited to participate in debriefing interviews to collect feedback regarding their experience with the CCC tool. We will also ask for feedback from 4-6 providers (2-3 medical oncologists and 2-3 PCP's) whose patients participated in the study. Due to time and budget constraints, we are only able to include a sample of patients and providers in our debriefing interviews.

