
This process will request contact information, including providing an address and telephone number to support following up after the follow-up survey has been emailed to participants if needed, sending the electronic gift card to participants via email, and contacting those interested in participating in debriefing interviews at the completion of the study.

Inclusion Criteria:

1. Ability to voluntarily provide written IRB-approved informed consent and communicate satisfactorily with the investigator, to participate fully in the study, and comply with all its requirements.
2. Women diagnosed with Stages 0-II breast cancer
3. Women who are currently receiving care from a breast oncologist at UMCCC
4. Women who are completing their primary treatment for breast cancer and transitioning into survivorship
5. Access and ability to use the Internet

Exclusion Criteria:

1. Women who are unable to speak and/or read English

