4.4.4. Patient Contacts: If a patient decides to participate, they will log into the CCC website using the unique assigned ID access code provided with the recruitment letter. Upon initial login, they will consent online, create their account (by inputting their email and phone number) and begin the baseline survey. They will receive one automated email reminder 2 days later if the baseline questionnaire is not completed, and up to 2 personalized phone contacts from the study coordinator within 14 days if the baseline questionnaire remains uncompleted. Upon completion of the baseline questionnaire, participants randomized to the intervention arm will receive weekly reminders via email, and possibly text messages if they opted into texting at account creation to make an appointment with their PCP. Three months from baseline completion, participants will receive a 1-week advance alert email (and a text if they opted in) for the follow-up questionnaire, followed by a second email alert in the next week, indicating the survey's availability on the CCC website. Participants will receive one automated email reminder 5 days later if the follow-up questionnaire is not completed. We will employ a modified version of the Dillman method, which includes up to 3 contacts for follow-up to maximize response rates and to identify non-respondents, that has proven to be successful in our previous work.

4.4.5. Debriefing Interviews: A sample of 8-10 patients who participated in the pilot testing and 4-6 of their physicians (2-3 medical oncologists and 2-3 primary care physicians) will be contacted via phone and invited to participate in debriefing interviews about the usefulness of the tool and future implementation strategies. A question will be included at the end of the follow-up survey which solicits their interest in being contacted after the study ends to discuss their experience with *ConnectedCancerCare* in more detail. For those who respond yes, we will select the first 8-10 people and contact them via phone to conduct a brief 20-minute audiotaped, interview (questions are in the Appendix), to gather their feedback about their experience with the tool.

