We will collect patient-reported outcomes in both the intervention and control groups. We will then explore whether the intervention (compared to control) is correlated with the following measures: Knowledge about continuing care guidelines measured by items used in our previous studies adapted to continuing care (categorical);²⁷ Preferences for team-based care (PCP or oncologist); Satisfaction with care measured by a care coordination question used in previous CanSORT studies tailored to the timing of transition (categorical);⁴⁰ Communication with providers about continuing care measured by an item from the SPARCCS adapted to the patient perspective (categorical).^{18,25} We will explore follow-up visit scheduling (yes/no) using patient-reported measure of whether or not they have scheduled a visit with their PCP since viewing the tool (or control). We will also ask patients whether they have seen their oncologist (yes/no) since viewing the tool and verify their responses using MiChart data.

Aim 3: Debriefing interviews

Guiding questions with prompts will be used to obtain patient and provider feedback (See Appendix for draft interview guide). Patients will be asked about the content of the tool, how they used the tool (or not), and whether it improved their care transition experience. In addition to these questions, providers will also be asked about their experience with the tool summary, how well it fit into their clinical practice, with the goal of understanding how to best imbed the tool into current clinical work-flow.

6. Procedures

6.1. Data Management: We use established human subjects' protection protocols that address the limited use of personal health information, transfer of de-identified datasets within our

institution, storage of information from various data sources and surveillance and response to adverse events. The primary risks of the study are related to breaches in confidentiality and patient concerns about the use of their medical information. We have a long track record of employing the highest standards of patient confidentiality. However, we will respond promptly to any patients or providers who contact the staff or investigators about any concerns related to the study.

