We will then explore comparing knowledge, satisfaction, communication and utilization among the 30-35 women who engaged with the tool to the 30-35 who received the standard of care using chi-square tests and two-sided student t-tests where appropriate. This is designed to be a pilot study to determine if patients who engage with tool score higher on key knowledge, communication, and satisfaction items compared to those who received the control.

Aim 3: Patient and Provider Debriefing Interviews

To better understand what worked and did not work following the pilot testing and the underlying mechanisms of the intervention, we will conduct a formative assessment with both patients and

providers who had a patient who enrolled in the study. All interviews will be audio recorded and transcribed and analyzed using Dedoose and NVivo software. The investigator team will review the transcripts to identify overall themes which will help to refine the tool as needed and guide the future implementation of it into a broader system-level tool used in clinical practice.

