Patient Recruitment for Pilot Testing Patients will be recruited through the Breast Cancer Clinic at the University of Michigan Rogel Cancer Center. Patients eligible for the pilot testing will be those who have recently finished their primary treatment for newly-diagnosed stage I-II female breast cancer and have scheduled their transition visit with the medical oncologist. For the pilot, we will recruit English speaking women with internet access.

Patient and Physician Recruitment for Debriefing Interviews: As stated in section 4.4, a convenience sample of 8-10 patients who participated in the intervention arm and answered that they were willing to be contacted for additional information regarding their experience with using the website on the follow-up survey will be invited to participate in debriefing interviews. We will contact these participants via email and invite them to participate in the debriefing interviews about the usefulness of the tool and future implementation strategies. Debriefing interviews will also be held with 4-6 of their physicians (2-3 medical oncologists and 2-3 primary care physicians) to obtain their views on the usefulness and usage of the tool by their patients and future enhancements.

Sources of Materials: All data to be used in this project will come from: 1) electronic patient surveys (pilot testing), 2) MiChart patient records (participant eligibility), and 3) patient and provider interviews. Survey data will include baseline data collected through the navigation tool, and then follow-up survey data for participants in the intervention three months later. Digital audio recordings will be taken during each physician and patient debriefing interview to be transcribed and analyzed.

8.1. Adequacy of Protection Against Risks: We use established human subjects' protection protocols that address the limited use of personal health information, transfer of de-identified datasets within our institution, storage of information from various data sources and surveillance and response to adverse events. The primary risks of the study are related to breaches in confidentiality and patient concerns about the use of their medical information. We have a long track record of employing the highest standards of patient confidentiality. However, we will respond promptly to any patients or providers who contact the staff or investigators about any concerns related to the study.

9. Data Safety and Monitoring

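### First-come selection of the 8-10 patient interviewees does not ensure that any low-rating or low-use woman is heard, and draws mainly on early enrollees

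*Combined protocol and SAP*

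**What the plan says.** Section 4.4.5 sets the sampling frame and the rule. On the frame: "A question will be included at the end of the follow-up survey which solicits their interest in being contacted after the study ends". Among those who say yes, "we will select the first 8-10 people and contact them via phone". Section 8 describes the same group as "a convenience sample of 8-10 patients who participated in the intervention arm and answered that they were willing to be contacted". Section 4.1 explains why only some are interviewed: "Due to time and budget constraints, we are only able to include a sample of patients and providers in our debriefing interviews".

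The purpose is in Section 7 under Aim 3: "To better understand what worked and did not work following the pilot testing". Section 5 under Aim 3 adds that patients will be asked "how they used the tool (or not), and whether it improved their care transition experience".

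The plan gives two timings. Section 4.2 speaks of "contacting those interested in participating in debriefing interviews at the completion of the study", whereas the table in Section 4.5 places the interviews 1-3 months after each woman's follow-up questionnaire.

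**The concern.** A woman reaches the interview only if she completes the 3-month survey, opts in at its end, and is among the first to do so. The first two steps probably tilt the pool toward women who used and liked the site. The third does nothing to offset that tilt. The rule could therefore return nine or so interviews with almost nobody who found the tool unhelpful or hardly opened it, which are the women Aim 3 most needs in order to explain failures.

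Rolling enrolment adds a second narrowing. Each woman's survey falls due three months after her own baseline, so being among the first volunteers largely means having enrolled early, and later enrollees would go mostly unheard.

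The reason given in Section 4.1 explains the number of interviews. It does not explain choosing by order of response.

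**Working it through.** The plan states no figure for this point. Its one precision figure (Section 7.1) concerns the acceptability proportion and does not enter here.

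**Inputs from the documents.** 8-10 patient interviews (I use 9); 30-35 women in the intervention arm; 9 months of enrolment; follow-up three months after baseline; acceptability items in the same survey that carries the opt-in question (Sections 4.4.3 and 4.4.5); page views and time on site captured (Section 5, Aim 1A).

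**Assumed inputs, because the documents give none.** N = 16-24 volunteers, of whom K = 4-6 are low raters; low raters respond at one half to one third the speed of the others; median delay for the others 5-14 days; enrolment uniform over 270 days.

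**Step 1: no speed difference.** Order of response is then unrelated to rating, and the number X of low raters among the first nine is hypergeometric: P(X ≤ 1) = [C(N−K, 9) + K·C(N−K, 8)] / C(N, 9).

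- N = 16, K = 4: (220 + 4 × 495)/11,440 = 0.19
- N = 20, K = 6: (2,002 + 6 × 3,003)/167,960 = 0.12
- N = 24, K = 6: (48,620 + 6 × 43,758)/1,307,504 = 0.24

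**Step 2: slower low raters, rolling enrolment.** Each volunteer's arrival time is enrolment day plus an exponential delay; the constant three months drops out. The first nine arrivals are taken (100,000 simulated runs per cell; ranges run from a 5-day to a 14-day median delay).

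| N, K, relative speed | P(X ≤ 1) | P(X = 0) | Latest enrolment month among the nine (mean) |
|---|---|---|---|
| 16, 4, 1/2 | 0.22-0.28 | 0.02-0.04 | 4.8-5.1 |
| 20, 6, 1/2 | 0.14-0.19 | 0.02-0.03 | 3.9-4.2 |
| 24, 6, 1/3 | 0.32-0.44 | 0.06-0.11 | 3.4-3.7 |

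So P(X ≤ 1) is about 14-44%, P(X = 0) about 2-11%, and on average the last of the nine enrolled 3.4-5.1 months into a 9-month recruitment.

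**Step 3: the opt-in filter.** Take 10 low raters among 30 women and 8 interviews drawn at random from volunteers, with 70% of the others volunteering. If low raters also volunteer at 70%, P(X ≤ 1) is 15%; at 35% it is 50%; at 20% it is 75%. With 10 interviews the figures are 6%, 36% and 65%. Differential opting-in can therefore matter more than response order.

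**Step 4: timing.** Enrolment of 9 months plus 3 months of follow-up gives the 12-month duration. If selection waits until every score is in, at about month 12, a woman enrolled at month 0 finished follow-up at month 3 and would be interviewed 12 − 3 = 9 months later. Only women finishing follow-up between months 9 and 11 would then fall in the 1-3 month window. A quota defined on ranks, such as the lowest third of scores, needs that wait. A cut-off fixed in advance does not, because each volunteer's score is known when she volunteers.

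**The case against.** The plan discloses a convenience sample, Aim 3 is thematic with no inference, and this is a pilot with limited resources. All of that stands and keeps the point minor.

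A reader might infer that the rule strongly favours fast, engaged users. The documents do not support that. If all volunteers are treated as starting the clock on the same day, the same three scenarios give P(X ≤ 1) of 39-73%, but that is not this study's enrolment. With rolling entry, fast responders make up 51-61% of those selected against 50% of all volunteers (simulations assuming 50-100% volunteering), so the speed effect is small. Much of the remaining risk is ordinary small-sample chance.

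A reader might also infer that the next version of the tool would rest mainly on satisfied users. That goes too far. Acceptability ratings are sought from the whole intervention arm, Section 7 uses any domain with a mean below 3 to guide adaptation, paradata are captured, and 4-6 physicians are interviewed. These sources can show where the tool is weak. They are less able to show why, which is the interviews' job.

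Finally, choosing among volunteers cannot reach women who skipped the survey or declined contact. That is correct, and it limits what any fix can achieve.

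**Conclusion.** The point holds as a modest design weakness. The first-come rule is in the current text, no other section replaces it, and it neither ensures a low-rating or low-use interviewee nor spreads interviews over enrolment, although Aim 3 needs to learn what did not work. The bias toward engaged users is a reasoned inference, and its size cannot be taken from the documents. Under the assumptions above, the chance that nine interviews include at most one low rater is about 14-44%, against 12-24% if low raters respond as fast as the rest. Most of any tilt would come from survey completion and opting in rather than from response speed.

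**What to change.** In Sections 4.4.5 and 8, replace first-come selection with a rolling purposive rule among willing intervention-arm women:

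- Reserve places, for example at least 3, for women whose summary acceptability score is below a cut-off fixed in advance, or whose page views or time on site are below a pre-set level. Section 5's summary threshold of 3 is one candidate; a higher cut-off may be needed if few women fall below it. Do not use tertiles.
- Spread places over the enrolment period, for example about three for each three months of recruitment.
- Invite each woman within the 1-3 month window of Section 4.5, and align Section 4.2 and the after-study wording of 4.4.5 with that window.
- Release unfilled places in order of response.
- Report as a limitation that survey non-completers and decliners are not represented.

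The same edit can reconcile phone contact (4.4.5) with email contact (Section 8), and state in 4.4.5 the intervention-arm restriction that Sections 4.1 and 8 already carry.

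The cost is a little coordinator tracking, with no extra interviews and no new data. Low raters may be too few or harder to reach. Interviews with the last enrollees would fall after month 12 (enrolment at month 9 plus 3 months of follow-up plus 1-3 months gives months 13-15), which the Section 4.5 window already implies for any late enrollee who is interviewed.

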4.5. Time and Events Table

Study Events	Pre-study (after completing primary treatment)	Time 1 (When viewing the website initially)	Time 2 3 months post-baseline questionnaire completion)	Time 3 1-3 months post-follow-up questionnaire completion)
Informed Consent	X			
Baseline Questionnaire	X			
Randomization		X		
View intervention or control website		X		
Follow-up questionnaire			X	
Debriefing Interviews				X

5. Measures

The measures described in detail below were selected after literature review, and were directly informed by our conceptual model and the results of our prior work and pilot data. The measures are described by specific aim below:

Aim 1A: Feasibility

Feasibility will be defined by the successful recruitment of at least 60 women with half randomized to the intervention website and half to the control website over a 9-month time period. Based upon positive response rates of patients in previous studies of survivorship interventions and the iCanDecide pilot trial, we anticipate approaching approximately 87 women in order to achieve a similar response rate of 80% enrollment (n=70). We will also assess the proportion of those successfully recruited who complete the baseline survey and the follow-up survey. In addition, we will capture paradata including participants' average number of page views, and average time on website.

Aim 1B: Acceptability

Acceptability and usability will be defined by asking participants in the intervention arm to rate their experiences with the tool on 5 point Likert-type scales, as follows: (1) CCC was easy to use, (2) CCC was helpful during my transition to survivorship, (3) CCC helped me think about when to see my PCP and when to see my oncologist, (4) I would recommend CCC to other patients, (5) The time it took to go through the website (6) The amount of info.

Based on our prior work, we will use a cut off of 50% of more reporting a score above 3 as acceptable within that domain. We will also examine the distributions within each domain and determine how we can make the next versions of the tool more acceptable to patients as needed. We will then create a summary score of acceptability by averaging the responses to the 6 items, with a score of 3 or more indicating the tool was acceptable to the majority of patients.

Aim 2: Exploratory patient-reported outcomes

We will collect patient-reported outcomes in both the intervention and control groups. We will then explore whether the intervention (compared to control) is correlated with the following measures: Knowledge about continuing care guidelines measured by items used in our previous studies adapted to continuing care (categorical);²⁷ Preferences for team-based care (PCP or oncologist); Satisfaction with care measured by a care coordination question used in previous CanSORT studies tailored to the timing of transition (categorical);⁴⁰ Communication with providers about continuing care measured by an item from the SPARCCS adapted to the patient perspective (categorical).^{18,25} We will explore follow-up visit scheduling (yes/no) using patient-reported measure of whether or not they have scheduled a visit with their PCP since viewing the tool (or control). We will also ask patients whether they have seen their oncologist (yes/no) since viewing the tool and verify their responses using MiChart data.

Aim 3: Debriefing interviews

Guiding questions with prompts will be used to obtain patient and provider feedback (See Appendix for draft interview guide). Patients will be asked about the content of the tool, how they used the tool (or not), and whether it improved their care transition experience. In addition to these questions, providers will also be asked about their experience with the tool summary, how well it fit into their clinical practice, with the goal of understanding how to best imbed the tool into current clinical work-flow.

6. Procedures

6.1. Data Management: We use established human subjects' protection protocols that address the limited use of personal health information, transfer of de-identified datasets within our

institution, storage of information from various data sources and surveillance and response to adverse events. The primary risks of the study are related to breaches in confidentiality and patient concerns about the use of their medical information. We have a long track record of employing the highest standards of patient confidentiality. However, we will respond promptly to any patients or providers who contact the staff or investigators about any concerns related to the study.

For pilot testing, the study coordinator will assign a unique study ID to each potential participant. A secure, unique ID access code generated by the website will be used by the participants when they log into the website. Access to the password protected, encrypted, study database will be restricted to the principal investigator and selected members of the study staff. For the physician interviews, the digital recordings and transcripts will also be de-identified and stored in password-protected files, which will only be accessible to the principal investigator and study staff. Patient and provider contact information will be kept in encrypted and password-protected files and used until the study and reporting is completed. The research data, which includes health-related data about the participants collected through the CCC intervention, will be stored for the required 7 years in a secured online server after which time the online data files will be electronically and securely deleted from the server, destroying all data.

Weekly meetings with [name] and the study staff will address any adverse events that could result from pilot study participation (e.g. increased anxiety) and patient and physician interview participation. These are anticipated to be rare and will be handled on an individual basis. Any adverse events will be reported to the IRBMED of the University of Michigan according to current IRBMED reporting guidelines.

7. Data Analysis Plan

Aim 1a: Feasibility

To determine feasibility, we will first assess whether we were successfully able to recruit 80% of our target population (N=87) into the study to achieve a maximum sample size of N=70. We will then generate descriptive statistics of the feasibility measures described above, including % of patients who complete each questionnaire, and average number of page views and time on website.

Aim 1b: Acceptability

The distribution within each of the 5 measures of acceptability will be determined and mean scores >3 within each domain will be examined. For any domain that has a mean score below 3, we will then use that information to inform future adaptations of the tool to increase the acceptability. The distribution of the acceptability summary score of will then be assessed and the proportion of patients with a score of 3 or more will be calculated.

Aim 2: Exploratory Patient-Reported Outcomes

We will then explore comparing knowledge, satisfaction, communication and utilization among the 30-35 women who engaged with the tool to the 30-35 who received the standard of care using chi-square tests and two-sided student t-tests where appropriate. This is designed to be a pilot study to determine if patients who engage with tool score higher on key knowledge, communication, and satisfaction items compared to those who received the control.

Aim 3: Patient and Provider Debriefing Interviews

To better understand what worked and did not work following the pilot testing and the underlying mechanisms of the intervention, we will conduct a formative assessment with both patients and

providers who had a patient who enrolled in the study. All interviews will be audio recorded and transcribed and analyzed using Dedoose and NVivo software. The investigator team will review the transcripts to identify overall themes which will help to refine the tool as needed and guide the future implementation of it into a broader system-level tool used in clinical practice.

